- 5 A comprehensive skin evaluation will be performed by the Investigator or designee. The skin examination should include a full body skin examination (head-to-toe skin examination). If any concerning lesions are identified during Screening, the patient should be referred to a dermatologist. Any concerning lesions identified during the Screening Period will be biopsied and results known to be benign prior to first dose of setmelanotide. If the pre-treatment biopsy results are of concern, the patient may be excluded from the trial. Additionally, any lesion or significant change in an existing lesion during the course of the trial must be evaluated by a dermatologist and biopsied, if clinically indicated in the opinion of the dermatologist.
- 6 Weight (kg) is to be measured at the clinic using the same scale throughout the trial or at home (during virtual visits) using the same scale provided to the patient as part of the clinical trial. Weight should be measured after patients have attempted to empty their bladders and after fasting for at least 8 hours. Patients are to wear light clothing or underwear and no shoes, with empty pockets and will be weighed at approximately the same time of day. All

measurements will be recorded to the nearest 10th of a Kg if reported with a digital scale, or half Kg with a mechanical scale. Whenever possible, the scale should be calibrated on a regular basis per manufacturer's specifications.

7 For patients ≥ 21 years of age, height is to be measured at Screening only. For patients aged < 21 years, height is to be measured at the time points listed in the SoA. Height (cm) will be measured, without shoes, socks or hats, using a wall-mounted stadiometer. The stadiometer should be calibrated by site personnel on a daily basis prior to height assessment. All measurements will be done in triplicate at each time point and recorded to the nearest half cm.

[REDACTED]

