In addition, safety data from more than 700 clinical trial participants through a cutoff date of 10 November 2021 demonstrate an acceptable safety profile across the populations studied, which include otherwise healthy subjects with obesity, patients with RGDO, and patients with acquired diseases resulting in obesity (e.g., hypothalamic obesity) arising from variants demonstrated or hypothesized to impact the hypothalamic MC4R signaling pathway. In these clinical studies, setmelanotide was administered QD at doses ranging from 0.5 to 5 mg and once weekly (QW) at doses ranging from 2.5 to 30 mg. Across the studies, the most common types of treatment-emergent adverse events (TEAEs) reported among setmelanotide-treated participants by Preferred Term included skin hyperpigmentation, nausea, and headache. Also common were TEAEs related to the injection site including injection site erythema, injection site pruritus, injection site induration, and injection site pain, each occurring in >10% of participants.

Data obtained to date in the setmelanotide clinical program demonstrate robust weight reduction and hunger suppression in patients with RGDO in which the leptin-melanocortin pathway upstream from MC4R is involved. In Phase 3 clinical studies of patients with POMC/PCSK1 and LEPR (PPL) deficiency obesity, setmelanotide demonstrated clinically meaningful and statistically significant body weight loss and hunger score reductions and was well tolerated. Similarly, in a Phase 3 trial of patients with BBS and Alström syndrome (AS), setmelanotide significantly reduced body weight and hunger and was well tolerated, with a predictable and therefore manageable safety profile.

In summary, setmelanotide's unique mechanism of action as a MC4R agonist enables a safe and highly targeted approach to treat patients with severe obesity due to genetic or acquired variants in the MC4R signaling pathway. By restoring impaired signaling in this pathway, setmelanotide can serve as an indirect form of replacement therapy, with the potential for significant improvements in hyperphagia and body weight and related measures.

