APPENDIX 2. CONSIDERATIONS FOR REDUCING PAIN AND DISTRESS IN THE PEDIATRIC POPULATION

Although the trial procedures and assessments required per protocol are classified as “No or Minimal Risk” according to the 2008 Guidance Document “Ethical Considerations for Clinical Trials on Medicinal Products Conducted with the Paediatric Population”, considerations for reducing pain and distress in participants <18 years of age are suggested below.

- The clinical trial may only be conducted if it exposes the person concerned to as little burden and other foreseeable risks as possible.
- Physical and emotional pain should be prevented as much as possible, and effectively treated when unavoidable.
- In order to minimize pain, distress, and fear, facilities should be appropriate to childcare, and the personnel should be trained to look after children and supervised by experienced health care professionals. Staff should be trained to communicate with both parents (or legal representative) and children. Generally, this would assume non-adult patients are being studied at experienced pediatric centers.
- For most procedures, the child should always be accompanied by a trial-related staff member who could provide reassurance. At the sign of distress and/or dissent, the procedure should be stopped. A short pause to allow the child to feel in control, further explanation, and an assessment of the situation may be needed to reassure the child, or to decide to definitely abandon the procedure at the discretion of the Investigator.
- In all situations, investigations/interventions should be limited to the minimum required for obtaining valid data and performed using size-/age-appropriate material and devices, including limiting in advance the number of attempts for sampling.
- Trial medication injections should only be performed by caregiver (or home health care professionals), unless the child is of suitable age and competency, and desires the ability to do so.
- Although almost all trial procedures are classified as low risk, risk should be continuously monitored and assessed by appropriate personnel.
- For assessments in which there is a psychological component, measures should be taken to minimize distress. For example, Tanner Staging assessments could utilize a diagram for the child to point to and indicate what stage they currently are, vs. having to have an examination without clothes.

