Low/Normal/High shift from baseline tables within stage will also be provided for hematology, coagulation and clinical chemistry. Normal/Abnormal shift from baseline tables within stage will also be provided for urinalysis.

Laboratory test results will be presented in data listings.

Pregnancy test will be presented in data listings.

E. Vital Signs

Vital signs include systolic and diastolic blood pressure (mmHg), heart rate (beats/min), respiration rate (breaths/min), and body temperature (°C). Vital signs will be obtained in the sitting position following at least 5 minutes of rest at each time point designated in the SOA.

All blood pressure and heart rate measurements will be taken in triplicate, approximately 2 minutes apart. The average of triplicate measurements will first be calculated within each patient then used in the summary statistics.

Summary statistics for actual values and changes from baseline within stage will be presented. Only in-person visits measurements will be summarized in table.

Vital sign data will also be presented in listing.

F. Physical Examination

Tanner staging data will be presented in listing.

G. Prior and Concomitant Medications

Prior and concomitant medications (CMs) will be coded using WHO-DD version September 2021.

G.1 Prior Medications

Prior medications are defined as medications with an end date prior to the first dose of study drug in Stage 1. Prior medications will be tabulated by Anatomic Therapeutic Chemical (ATC) Level 2 classification and Preferred Term (PT) by treatment group and overall. A patient having more than one medication within the same ATC Level 2 or preferred term will be counted only once for that ATC Level 2 or preferred term.

G.2 Concomitant Medications

Concomitant medications are defined as medications which are taken during the course of study stage. A detailed definition will be as following:

Stage 1

A medication will be considered a concomitant medication in Stage 1 as following:

- If the end date is completely missing and the medication start date is before the Stage 2.
- Or the medication start date is before the Stage 2 treatment administration and end date is on or after Stage 1 treatment administration or it is ongoing.

Stage 2

A medication will be considered a concomitant medication in Stage 2 as following:

- If the end date is completely missing
- Or the medication is either ongoing or end date is on or after Stage 2 treatment administration.

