- Any medications happening after the dosing date at visit 14 will not be considered as concomitant medication in stage 2

Concomitant medications will be tabulated by ATC Level 2 classification and PT by stage. A patient having more than one medication within the same ATC Level 2 or preferred term will be counted only once for that ATC Level 2 or preferred term.

A listing of prior and concomitant medications will be provided.

H. Concomitant Procedures

Concomitant procedures data will be listed by stage. The definition of stage will follow adverse events in IX.B.

I. Skin Examination

A comprehensive skin examination will be performed by the Investigator at the time points designated in the SOA.

The skin examination should include a full body (head-to-toe skin examination).

Frequency count of most severe outcome across all skin regions within patients will - be provided by stage and visit. The severity of the outcome is rated as Abnormal, CS > Anormal, Not CS > Normal > Not Done.

Also, the frequency count by skin region with abnormal result will be provided.

All skin examination data will be presented in listing.

J. Hyperpigmentation

Hyperpigmentation form will be administered at postbaseline visits.

All hyperpigmentation data will be presented in listing.

K. Sexual Function

Sexual function forms have different versions between male and female. All sexual function data will be presented in listing by version.

L. Electrocardiogram

A single 12-lead electrocardiogram (ECG) is performed at the visits designated in the SOA.

ECG measurements include PR interval (msec), RR interval (msec), QRS interval (msec), QT uncorrected (msec), QT corrected with Bazett's formula (msec), QT corrected with Fridericia formula (msec). Summaries of actual values and changes from baseline of these measurements will be presented.

A frequency and percentage table of normal, abnormal not clinically significant and abnormal clinically significant for overall ECG evaluation will be tabulated.

ECG data will be presented in listing.

M. Columbia-Suicide Severity Rating Scale (C-SSRS)

The C-SSRS that will be administered to patients ≥ 6 years of age according to the SOA.

There are two versions of the C-SSRS forms:

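### The SAP skin table reports an incomplete examination with no abnormality seen as Normal, and plans no count of findings that are new since Screening

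*SAP*

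**What the plan says.** SAP IX.I plans three outputs for the skin examination.

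- A patient-level table: "Frequency count of most severe outcome across all skin regions within patients will - be provided by stage and visit". The order used to pick the worst result is "The severity of the outcome is rated as Abnormal, CS > Anormal, Not CS > Normal > Not Done". (The misspelling is of no consequence.)
- A table by region: "the frequency count by skin region with abnormal result will be provided".
- A listing of all skin data.

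The section describes the examination as full-body, head to toe. It names no shift table, no change from baseline and no count of new or worsened findings.

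A reference examination exists. Protocol Table 1 schedules the skin examination at Screening, at V5 and V7, and at early termination. Table 2 schedules it at Stage 2 Entry, end of treatment, early termination and bridging visits, and at the end-of-study visit if that is held in person. Patients can enter with a skin abnormality. Table 1, footnote 5 says: "Any concerning lesions identified during the Screening Period will be biopsied and results known to be benign prior to first dose of setmelanotide".

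Other SAP sections treat comparable data differently. For hematology, coagulation and chemistry, IX.D says "Low/Normal/High shift from baseline tables within stage will also be provided", and it adds a normal/abnormal shift for urinalysis. The C-SSRS also gets a shift from baseline. Injection-site percentages use only patients assessed at the visit. PHQ-9 scores are summarised only when all nine items were answered.

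**The concern.** Two separate problems follow from the patient-level rule.

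**Completeness.** An order that places Not Done below Normal matters only when some regions were examined and others were not. In that case the rule lets the examined regions speak for the whole body, so the reader of the table cannot tell a full normal examination from a partial one. Partial examinations are foreseeable. Patients may be as young as 6, and Protocol Appendix 2 says of patients under 18: "At the sign of distress and/or dissent, the procedure should be stopped".

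**New versus pre-existing.** A worst-result count at each visit describes who has any abnormality, not who has acquired one. Once a patient is in an abnormal category, further findings of the same or lower rank cannot move that patient. Stage 2 adds a complication, because every randomized patient has already had about 16 weeks of drug. Counts by arm then mix findings present at entry to the trial, findings acquired in Stage 1 and findings acquired in Stage 2.

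At stake is whether the tabulated skin examination can be read as a treatment-emergent safety summary.

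**Working it through.** The plan gives no figure to reproduce, so the check applies the SAP rule directly.

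**Inputs.** From SAP IX.I: patient category = maximum over regions, scored CS (clinically significant) = 3, Not CS = 2, Normal = 1, Not Done = 0. The documents do not give the number of regions. I assume 5; the conclusions do not depend on it.

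**1. Partial examinations with no abnormality seen.** Let k of 5 regions be normal and the rest not done.

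| k | Category |
|---|---|
| 0 | Not Done |
| 1, 2, 3 or 4 | Normal |
| 5 | Normal |

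One examined region gives the same entry as five.

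**2. All partial patterns.** Patterns with at least one region, but not all, not done: 4^5 − 3^5 − 1 = 1,024 − 243 − 1 = 780. Of these, the patterns with no abnormality number 2^5 − 2 = 30, and all 30 are reported as Normal. The other 750 contain an abnormality and are reported as abnormal. These are counts of patterns, not of patients, and imply no rate.

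**3. New Not CS finding in a previously normal region, entry abnormality persisting.** For each of the 5 possible regions, the other four must contain at least one abnormality: 4^4 − 2^4 = 256 − 16 = 240 patterns. Total 5 × 240 = 1,200. The category changes in 0 of 1,200, because the maximum is already at least 2 and the new finding scores 2.

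**4. Entry abnormality resolves while a new Not CS finding appears.** If the entry finding was Not CS, the category is unchanged. If the only CS finding resolves, the category moves from CS to Not CS and looks like an improvement.

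**5. What the by-region count shows.** It rises by 1 if the new finding is in a previously normal region. It does not change if that region was already abnormal. The total over regions does not change if another region resolves at the same time. In no case does it label a finding as new.

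**6. Illustration with assumed counts.** Take 100 patients, 30 with Not CS at Screening and 70 normal. Let m of the 30 gain a Not CS finding in a previously normal region, with no other change.

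- SAP patient-level abnormal count: 30 at Screening and 30 at follow-up, for every m from 0 to 30.
- Shift table of the worst category: 30 from Not CS to Not CS, for every m.
- Count of patients with a newly abnormal region: m, for example 20 when m = 20.

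This shows the mechanism. It does not estimate its size.

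**The case against.** The strongest reply is that most of what matters is caught elsewhere.

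- An abnormality seen in a partial examination is still counted as abnormal.
- The table is by visit and Screening is a skin-examination visit, so Screening totals may appear in it.
- The by-region table can register a finding in a new region, and the listing holds everything.
- Protocol 8.9.2 requires clinically significant changes on physical examination to be recorded as adverse events, and these are tabulated.
- Lesions arising or changing during the trial go to a dermatologist whatever the table shows (Protocol Table 1, footnote 5, and 8.9.3).
- SAP V.I gives the DSMB unblinded skin-examination and hyperpigmentation data.
- Appendix 2 covers only patients under 18, and it provides for a pause and reassurance before a procedure is abandoned.
- Protocol 10.3 promises change from baseline only for vital signs and laboratory results, so the documents do not contradict each other.

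All of this stands, and it limits the point to summary reporting. It does not remove it. Screening totals compare groups, not the same patient over time. The region count and the listing do not summarise what is new. New findings judged not clinically significant need not reach the adverse event tables by the 8.9.2 route.

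A reader might also infer that the main known skin effect of the drug would be hidden. The documents do not support that. Protocol 3.1 lists skin hyperpigmentation as an adverse event preferred term, a route that is tabulated here, and SAP IX.J gives hyperpigmentation its own form and listing.

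**Conclusion.** The point holds as a reporting defect in a descriptive safety table. The stated rule labels an incomplete examination with no abnormality seen as Normal. The planned tables also cannot separate findings present at entry from findings that are new. The primary endpoint and the individual safety procedures are unaffected.

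The size is unknown. The documents give no rate of incomplete examinations, of abnormality at Screening or of new findings. A reader might infer that Normal results are overstated by a material amount, or that a particular share of new findings goes unseen. Neither can be derived from the documents.

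The conclusion on new findings assumes that the entry abnormality persists or was itself Not CS. The proposed comparison assumes that the Screening examination is recorded by the same regions as later ones; the SAP's wording suggests this, but the form is not shown. Given how little the correction costs, it should be made.

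**What to change.** In SAP IX.I:

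- Count a patient as Normal at a visit only if every region was examined and normal. Show patients with no abnormality seen and at least one region not done as Incomplete. Keep Not Done for visits where no region was examined.
- Add, by stage and visit, the number of patients with at least one region newly abnormal, or worsened to CS, compared with the same region at Screening. For Stage 2, give the same count compared with the Stage 2 Entry examination. Display Stage 2 by arm, which SAP V.N already provides for.
- State how a region not done at the reference examination is handled, for example as not assessable for change.

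A shift table of the patient-level worst category is not enough, because Not CS to Not CS would still hide the new finding (step 6). The by-region comparison has its own limit: it misses a second Not CS finding in a region already abnormal, so the listing should stay.

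The cost is SAP wording and one or two more tables from examinations already scheduled. A few examinations would move from Normal to Incomplete. No visit, procedure or clinical rule changes.
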